Psychosocial counselors (n=4 total): Trained psychosocial counselors will be identified to administer counseling sessions for both the AFB and EFB arm. We will recruit 2 female counselors for each primary intervention arm clinic to complete up to 4 individual prenatal counseling sessions and up to 2 postnatal group sessions (approximately 100 counseling sessions per counselor total over 4-6 months, and ~ 20 counseling sessions per counselor per month). Group counseling will be offered on multiple days; each group will have 5-8 women attending 2 sessions.

Research Assistants (n=3): Trained research assistants will be hired to conduct participant screening and to complete baseline and 6-month data collection with all participants at each of the five study clinics. Research assistants will spend the majority of their time in each of the three primary study sites and rotate between the remaining two clinics as needed.

Supervisors (n=2): Supervision for counselor will be provided by the study mental health professionals (n=2).

F6. Pilot Trial Arms

We have adapted the Friendship Bench intervention to meet the particular needs of HIV-infected women with PND and enhanced it to additionally support engagement in perinatal HIV care. We will conduct a pilot trial, comparing Enhanced Friendship Bench (EFB), to enhanced standard care (ESC).

1. Arm 1: Adapted Friendship Bench (AFB - DROPPED) – [Note: This arm is no longer included in the trial as of protocol v3.1, but this text is retained to aid with understanding Arm 2.] The existing Friendship Bench intervention protocol has been adapted to address the unique needs of HIV-infected women. AFB will include 4 individual prenatal counseling session (in-person or by phone) and 2 group postnatal counseling sessions. No specific retention support will be provided, but participants may identify barriers to engagement in HIV care to address during their pre- or postnatal counseling sessions.

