Prenatal counseling sessions (n=4) will be facilitated by psychosocial counselors and are designed to align with the WHO's recommended 4 antenatal care visits. However, since many women in sub-Saharan Africa do not attend all 4 antenatal sessions, prenatal counseling sessions can occur outside antenatal visits, including by phone. The first session includes three components called Opening the Mind, Uplifting, and Strengthening, with subsequent sessions building on the first. Opening the Mind refers to the therapeutic process by which, through asking questions, clients are encouraged to open their minds to identify their problems, choose one to work on, identify a feasible solution, and agree on an action plan through an iterative process guided by the counselor. Each structured session lasts 30-45 minutes and will be conducted in a private clinic room, or by phone, in participant's local language (Chichewa). Participants will receive up to 4 text messages, phone calls, or both during their treatment course to reinforce the PST approach and encourage them to follow their action plan. After 4 sessions of individual prenatal therapy, the counselor can refer participants not improving or with suicidal ideation to a supervisor trained in mental health to reassess and manage the case. Case management may include additional counseling or pharmacotherapy, at the discretion of the managing clinician.

Postnatal counseling sessions (n=2) will be facilitated by a psychosocial counselor. In Malawi, HIV-infected women transition from receiving HIV care at an antenatal clinic to an ART clinic, typically by 6 weeks postpartum. Postnatal group counseling session will occur after a woman has transitioned to receiving care at an HIV clinic. In the Adapted Friendship Bench arm, women will be invited to attend 2 postnatal group-counseling sessions. Postnatal group counselling sessions will be scheduled to coincide with a woman's

regularly scheduled ART visits. All sessions will include 5-8 women and will take place on a variety of days to accommodate women's varying ART clinic appointment schedules. Group counseling sessions will last ~60 minutes and will be conducted in a semi-private clinic location in Chichewa.

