2. Arm 2: Enhanced Friendship Bench (EFB) - EFB will include all elements of AFB, but will additionally integrate retention strategies. Retention Strategy 1. Strengthening social support: To provide additional social support for participants, we will add one (optional, recommended) "person important to me" session to the AFB. At this session, the participant will be invited to bring with her to one session a person of her choice who can be a support to her in managing both her HIV and/or depression, such as a partner, friend, or companion. To reduce the risk of inadvertent disclosure of one's HIV or depression status, prior to this social support session, we will ask all participants beforehand whether the person that she identified knows her HIV and depression status. If they do not, we will discuss risks with her before proceeding as she wishes. The social support session may be conducted in person, in a private clinic room, or by phone. Retention Strategy 2. Home visits: In our formative research, perinatal women discussed their barriers to attend clinic visits to pick up their meds, especially during late stages of pregnancy and immediately following birth. One common suggestion the women discussed to support HIV care engagement was home visits when they were unable to attend clinic. To assist women with receiving their medication during late pregnancy and postpartum, we will conduct up to six home visits in the EFB arm. To preserve patient confidentiality, prior to initiating home visits the participant and her counselor will agree on a "cover story" for the counselor's identity when she comes to visit ("This is my aunt from..."). The counselor will be able to deliver her medications. The counselor will also conduct a counseling session, if they have enough privacy to do so. Home visits may begin monthly starting in the third trimester and continuing through up to 6 months postpartum. The participant may decline home visits, if for example she is concerned that the home visit would pose a risk for her with her community or family.

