3. Enhanced Standard Care (ESC). Standard care for mental health in public facilities in Malawi includes options for basic supportive counseling by the primary provider or nurse, medication management by the primary provider, referral to the clinic psychiatric nurse or mental health clinic (most clinics have either an assigned psychiatric nurse or a mental health clinic that visits on a rotating basis), or in more severe cases referral to the psychiatric units at tertiary care hospitals (in the Lilongwe region, this is Bwaila Hospital). For this study, standard care will be enhanced by a trained study research assistant who will provide mental health screening; basic psychoeducation education on common mental disorders; and (if indicated) facilitation of referral to the clinic's psychiatric nurse or mental health clinic or to Bwaila Hospital. The RA will also ensure that the patient sees a nurse or clinical officer that day to evaluate whether the referral plan is appropriate and to ensure that the participant is safe to go home. The research assistant will have up to 3 follow-up contacts with the participant to assess whether she has followed up on recommended referrals or treatment plans and to assess whether any further outreach is indicated.²⁴

F7. Intervention delivery and supervision – Our adapted and enhanced counseling interventions will be delivered by trained psychosocial counselors. Prior to study enrollment, counselors will be trained to deliver the Adapted Friendship Bench and Enhanced Friendship Bench interventions. During the pilot, counselors will be supervised by District Health Promotion Officers and the study psychiatrist.

- **Setting:** During the prenatal period, individual counseling sessions will be facilitated by counselors in a private location within the antenatal clinic, or via phone. Due to issues around stigma and disclosure for both HIV-infected and depressed women, individual, rather than group, counseling sessions will be preferable to ensure patient privacy in the antenatal clinic which serves the general pregnant population. During the postnatal period, group counseling sessions will be facilitated by counselors at a semi-private location on the grounds of ART clinics. The group counseling sessions will be described as "friendship groups", with no mention of PND, to reduce possible stigma associated with depression. ART clinics serve only HIV-infected women, reducing concerns about HIV-related stigma or disclosure.

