- **Training:** counselors serving as counselors from both antenatal and ART clinics will attend a 2-week training. Topics included in the training will be PND, counseling skills, problem solving therapy, and self-care. [name] and members of his team will deliver the training. All training sessions will be audio-recorded for fidelity and assessed using a checklist to ensure the counselors had covered all the critical components.

- **Supervision:** counselors will be supervised and supported by the study's two mental health professionals ([name] and [name]) who will be contacted in the event that a client presents with very high scores on the EPDS or suicidality. A Friendship Bench trainer will provide weekly group supervision for counselors.

F8. Intervention Delivery and Data Collection. Prior to launch, each of the three primary clinics will be randomly assigned to Adapted Friendship Bench (AFB), Enhanced Friendship Bench (EFB) or enhanced standard care (ESC), with the exception of the fourth and fifth clinics which will individually randomize eligible participants to one of the two remaining study arms.

Screening and Enrollment HIV-infected women who are initiating, re-initiating, or continuing ART during pregnancy under the Option B+ will be informed about the study by their provider and invited to participate. Screening and enrollment procedures will take place on the same day as a woman's ANC visit. Women who consent to participate (Appendix 1) will be given an initial screening for perinatal depression or anxiety using the Patient Health Questionnaire (PHQ)-2 and/or the Generalized Anxiety Disorder (GAD)-2 as a part of routine antenatal care. Women who show symptoms perinatal depression or anxiety will be asked to complete the Edinburgh Postnatal Depression Scale (EPDS) and/or the Self-Reporting Questionnaire (SRQ)-20 with a trained psycho-social counselor to confirm symptoms (Appendix 2). Women who screen positively on either the PHQ-2/GAD-2, the EPDS (≥ 10) or SRQ-20 (≥ 8) will be invited to participate. Women screening positive for depression who choose not to participate will be referred to a mental health provider for care.

Study Visits (n=2 for participants in all arms)

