6-month Postpartum Visit: At 6 months postpartum, HIV-infected women will be asked to complete the EPDS and SRQ-20 either in-person or by phone. Viral load measures for all HIV-infected women will be collected by study personnel at 6 months postpartum. Information on HIV appointment attendance and infant HIV testing during the first 6 months postpartum will be collected from a participant's medical record, as we are doing in our ongoing USAID project. Information on infant anthropometry (length, weight, head circumference), infant physical health (presence of respiratory illness, diarrhea, and immunization records) and infant development, assessed using the Observation of Mother-Child Interaction (OMCI) guide, the PAMANED Study Family Care Indicators Questionnaire in Chichewa, and the WHO Indicators of Infant and Young Child Development (IYCD) Item guide, which have been validated for use in children as young as 4 months of age, will also be collected (Appendix 2). The OCMI portion of the 6 month postpartum visit will be video-recorded to review the fidelity rating after the visit has occurred. HIV-infected women, counselors and supervisors will be asked to complete a brief exit interview either in-person or by phone to assess the feasibility and acceptability of the intervention.

Counseling Sessions (EFB n= up to 7; ESC, n=0):

Women will be followed from study enrollment at their ANC visit through 6 months postpartum. Women in the

AFB and EFB arms will receive approximately 4 prenatal individual counseling sessions and approximately 2 optional, but recommended postnatal group counseling sessions (n=up to 6 counseling session). Women in the EFB arm will receive up to the same number of counseling sessions (4 prenatal and 2 postnatal) as women in the AFB arm, with an additional social support session described in section F6 (n=up to 7 counseling sessions). Women in the ESC arm will not receive counseling sessions, but will receive psychoeducation from a trained research assistant, referrals as needed, and follow-up calls to assess whether referrals were acted on and whether any further unmet mental health needs remain (n=0 counseling sessions). Counseling sessions will take place every 1-2 weeks at the antenatal care clinic, or via phone, during the prenatal period and approximately monthly during the postnatal period to coincide with routine ART refill visits.

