Data Collection: At each counseling session (prenatal and postnatal) women will be asked to complete the EPDS and SRQ-20 to assess their mental health status.

F9. Outcomes – The primary goal of this R34 application is to evaluate the feasibility, acceptability, and fidelity of a counseling intervention to improve PND and engagement in HIV care among HIV-infected women. Recognizing the small sample size, indicators of preliminary effectiveness of the intervention for mental health and engagement in care outcomes will be reported as secondary outcomes. Primary and secondary outcomes will be assessed at 6 months postpartum and compared across the study arms.

F9.a. Primary Outcomes:

Feasibility will be defined as the ability to successfully enroll and retain HIV-infected, depressed women in the pilot intervention. Feasibility will be assessed as the number of women enrolled, a comparison of planned to actual enrollment and reasons for non-enrollment, and the proportion of women retained in each arm at 6 months postpartum.

Acceptability will be defined as the ability to deliver a culturally and resource-appropriate intervention. Acceptability will be assessed through brief exit interviews among a subset of HIV-infected women. Exit interviews will include both closed and open-ended questions and will assess how easy the intervention was to participate in or deliver, the perceived usefulness of the intervention, and suggestions for improvement.

Fidelity will be defined as adherence to the intervention protocol. Fidelity to session content for both individual and group counseling sessions will be assessed by members of the Friendship Bench team (DHO or study psychiatrist), by using a checklist of intervention characteristics either during direct monitoring or using audio recording of up to 3 randomly chosen sessions per counselors. Scoring either 'meeting expectations' or 'exceeding' expectations' on at least 80% of applicable checklist items during each session will be considered fidelity to the intervention protocol.

F9.b. Secondary Outcomes: Secondary outcomes will be used to provide preliminary information about effectiveness at 6 months postpartum, taking into consideration the limited sample size for the pilot project.

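### F6 and F7 give different triggers for escalating suicidal ideation in the counseling arm: one follows a count of four sessions, the other follows the event itself

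*Combined protocol and SAP*

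**What the plan says.** Two places in the protocol deal with suicidality that comes to light in a woman receiving counseling.

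- **F6, Arm 1, prenatal counseling sessions:** "After 4 sessions of individual prenatal therapy, the counselor can refer participants not improving or with suicidal ideation to a supervisor". The supervisor is to be someone trained in mental health, who reassesses and manages the case.
- **F7, Supervision:** the two mental health professionals who support the counselors are people "who will be contacted in the event that a client presents with very high scores on the EPDS or suicidality". No minimum number of sessions is given.

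The F6 sentence stands under the AFB arm, which was dropped, but it still applies. The note on that arm explains that "this text is retained to aid with understanding Arm 2", and the Arm 2 description says that "EFB will include all elements of AFB, but will additionally integrate retention strategies". The Arm 2 description has no escalation rule of its own.

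On schedule and measurement, F8 says: "Counseling sessions will take place every 1-2 weeks at the antenatal care clinic, or via phone, during the prenatal period". It adds: "At each counseling session (prenatal and postnatal) women will be asked to complete the EPDS and SRQ-20 to assess their mental health status".

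On who supervises, F4 says: "Supervision for counselor will be provided by the study mental health professionals (n=2"). The opening paragraph of F7 instead names the study psychiatrist together with District Health Promotion Officers.

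**The concern.** A counselor who finds suicidal ideation at an early session has two texts to work from. F6 makes referral something she *can* do, after a fourth session. F7 says that the professionals *will* be contacted when the problem presents. The texts differ in trigger (session count or event) and in force (optional or directed), and possibly in the person to be reached.

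What is at stake is a participant-safety instruction. Every woman enters the trial because she screened positive for depression or a common mental disorder, and her symptoms are assessed again at each session. Ideation that surfaces before session 4 is therefore a foreseeable situation. For that situation the protocol should give counselors one reading.

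**Working it through.** The plan states no figure for this delay, so there is none to reproduce. The check sets the two texts side by side and then applies simple arithmetic to the session schedule.

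**Step 1. Does the F6 sentence govern EFB women?** Yes. The AFB text is kept to explain Arm 2, EFB takes over every AFB element, and no separate EFB rule replaces it.

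**Step 2. Do the two texts differ?**

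| | F6, prenatal sessions | F7, Supervision |
|---|---|---|
| Trigger | four individual sessions completed | client presents with suicidality or a very high EPDS score |
| Force | permissive (*can*) | directive (*will*) |
| Action | refer, for reassessment and case management | contact |
| Person | a supervisor trained in mental health | the two study mental health professionals |

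As the F6 sentence is built, its opening condition covers both groups that it names: women who are not improving and women with ideation.

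**Step 3. Is there an opportunity before session 4?** Yes. The EPDS and SRQ-20 are completed at each session, so a concern can surface at session 1, 2 or 3.

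**Step 4. How large can the gap be?** Inputs: four prenatal sessions (F6) and an interval of 1 to 2 weeks (F8). If ideation is first seen at session *k*, then

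weeks from session *k* to session 4 = (4 − *k*) × interval.

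- *k* = 1: 3 × 1 = 3 to 3 × 2 = 6 weeks
- *k* = 2: 2 × 1 = 2 to 2 × 2 = 4 weeks
- *k* = 3: 1 × 1 = 1 to 1 × 2 = 2 weeks
- *k* = 4: no gap

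**Step 5. Does another section settle it?** In the text available, suicidality appears only in these two places. The sections on potential risks and protection against risk, and the data safety and monitoring plan, deal with confidentiality and social harms.

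**The case against.** The strongest reply is that the texts are in tension but do not exclude each other. F6 is permissive and does not forbid earlier contact, and F7 has no session threshold, so a counselor can obey both. A delay arises only if she follows F6 and overlooks F7. The session condition in F6 might also have been meant only for women who are not improving. Referral for case management and contact after an event could be two separate steps, possibly to different people. F7 gives a trigger and no deadline. All of this stands. It means that delay is a possible reading and not an instruction. It does not remove the problem, because the protocol nowhere says which of these readings is intended.

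There are also safeguards. Women who screen positive are referred to mental health care (section J), and counselors have weekly group supervision (F7). These may shorten a real delay. However, the referral acts on the screening result, and the supervision text states no rule for ideation found during counseling.

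Three stronger readings are tempting, and the documents do not support them:

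- **That the arms differ in how fast suicidality is handled.** For ESC women, F6 says: "The RA will also ensure that the patient sees a nurse or clinical officer that day". That review concerns whether the referral plan is suitable and whether the woman is safe to go home. It does not mention suicidality, and ESC women have no counseling sessions. Comparing it with the F6 counseling text sets an initial review against a later step during treatment.
- **That the treatment comparison is affected.** This would need the between-arm difference just described, which is not shown. The screening referrals are also not limited to one arm.
- **That all 40 EFB women planned for the randomized phase are affected.** The conflict matters only for those who show ideation before session 4.

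**Conclusion.** The point holds as a conflict of wording between F6 and F7 on a safety matter. Read literally, F6 could lead a counselor to act later than F7 indicates. The upper bound is about 3-6 weeks, reached only when ideation first appears at session 1. It falls to 2-4 weeks from session 2 and 1-2 weeks from session 3.

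The figures assume that the woman completes four sessions at the stated spacing, that the F6 session condition covers ideation as the sentence is written, and that F7 means contact at the time of presentation, which is its plain reading and not a stated deadline. The number of women concerned cannot be estimated from the documents. No position is taken here on which timing is right.

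**What to change.** Reconcile the F6 sentence on prenatal sessions with the F7 Supervision paragraph, so that the protocol:

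1. states one consistent timing for suicidality in the counseling arm, wherever it is mentioned, and makes plain that this text governs EFB women;
2. says whether *refer* and *contact* are one step or two;
3. names who is contacted, since F4 and the F7 Supervision paragraph point to the two mental health professionals while the opening of F7 names other supervisors.

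The clinical team must decide which timing applies. The change costs protocol wording and a line in counselor training, with no extra staff or visits.

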In Malawi, all pregnant women presenting for care receive opt-out HIV testing at their first antenatal care visit. Women who test HIV+ undergo adherence counseling and start ART the same day. PND screening and assessment are rare to nonexistent at antenatal/ART clinics in Lilongwe, as in most clinical settings in Malawi.

UNC Project in Lilongwe will serve as the administrative home for the study and has longstanding relationships with Bwaila FHU, antenatal/ART clinics in Lilongwe, and the Ministry of Health.

F4. Study Population:

Women (92 total): As of this protocol v3.2, we have recruited a total of 12 women from our original 3 clinics. As we launch activities at our two new clinics and reduce to 2 arms, we will seek to recruit 40 new participants per arm or 80 new participants total, for a total enrollment of 92 participants. All 92 women will contribute to analyses of feasibility and acceptability, but only the new 80 women will contribute to between-arm comparisons due to the differences in sites.

We will include 92 HIV-infected, depressed women initiating, re-initiating, or continuing ART who engage in ANC and are identified with antenatal depression at ≤ 34 weeks gestation to allow sufficient time for approximately 4 prenatal counseling sessions and approximately 2 postnatal counseling sessions. Women with a score ≥ 10 on the EPDS^{48,49} and/or ≥ 8 on the SRQ-20 will be considered to be depressed and will be invited to participate.

Inclusion criteria:

- HIV-infected, pregnant women initiating, re-initiating, or continuing ART during antenatal care (ANC)
- ≤ 34 weeks gestation to allow sufficient time for approximately 4 prenatal counseling sessions and approximately 2 postnatal counseling sessions.

- Screened positive for depression with a score ≥ 8 on the SRQ-20
- At least 18 years of age

Feasibility of recruitment – Approximately 30 HIV-infected women initiate or re-initiate ART monthly at each of the study sites, or 150 women over 6 months, with ~90% presenting at ≤ 30 weeks. Based on our group's systematic review³⁴, we conservatively estimate 30% of HIV-infected women will have antenatal depression, suggesting that enrolling ~6 women per site per month is feasible. Utilization of two additional clinics will aid in timely participant recruitment should enrollment at the three primary sites lag behind expected targets.

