I. Impact and Future Directions: PND is extremely common in sub-Saharan Africa and negatively affects women, infants, and communities. For HIV-infected women, PND may also adversely affect perinatal engagement in HIV care, putting them at an even greater risk of poor HIV outcomes. Resource-appropriate interventions to address PND, and its possible impact on engagement in HIV care, are urgently needed. The information gathered in this proposal will lead to an R01 application to test our intervention in a randomized controlled trial.

J. Protection of Human Subjects

This Human Subjects Research meets the definition of clinical research. The data collection and analyses outlined in this proposal will be reviewed by the University of North Carolina Institutional Review Board, in the U.S., and the Malawi National Health Sciences Research Committee (HSRC) before any data collection or analysis occurs.

The study will also be reviewed and informed by the existing community advisory board (CAB) of UNC Project in Malawi. The CAB will review the study protocol prior to implementation and provide feedback. The CAB meets monthly.

1. Risks to Human Subjects

a. Human Subjects Involvement and Characteristics

In our pilot study, we will recruit 92 prenatal HIV-infected women who consent to participate and screen positive for mental health disorders during pregnancy on the EPDS or SRQ-20 questionnaires, indicating perinatal depression (PND) or common mental health disorders. Psychosocial counselors (n=4), research assistants (n=3), and supervisors (n=2) will be considered a secondary population. The goal of our study is to evaluate the feasibility, acceptability, and fidelity of the enhanced Friendship Bench intervention to improve PND and engagement in HIV care among HIV-infected women. Women will be recruited from the Lumbadzi, Mitundu, Nathonje, Area 18, and Bwaila healthcare centers in Lilongwe, Malawi when they present for prenatal care initiation and are HIV-positive. All women who screen positive for depression will be referred for mental health treatment to the nearest provider.

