Rational for including pregnant women: Option B+ is a program of the Malawi Ministry of Health to provide lifelong ART to all HIV-infected women who are pregnant. A critical component to the success of Option B+ is keeping women engaged in HIV care – something that has emerged as a challenge since Option B+'s inception in Malawi. Women with PND may be at an increased risk of disengaging from HIV care. Our project includes pregnant women in an effort to improve treatment options for PND among this population, with the goal of also improving engagement in HIV care and ultimately the effectiveness of Option B+.

The study characteristics of the study population are expected to be similar to those of all HIV-infected, peripartum women with PND in public healthcare centers in Lilongwe, Malawi.

Participants who live outside of the Lilongwe District or are less than 18 years old will be excluded.

b. Sources of Materials

All data will be gathered specifically for the purpose of the study. For Aim 1, women will undergo a screening and enrollment visit (baseline), up to six counseling sessions, and will have outcomes assessed at 6 months.

Screening and Enrollment HIV-infected women who are initiating, re-initiating, or continuing ART during pregnancy under the Option B+ will be informed about the study by their provider and invited to participate. Screening and enrollment procedures will take place on the same day as a woman's ANC visit. Women who consent to participate (Appendix 1) will be given an initial screening for perinatal depression or anxiety using the Patient Health Questionnaire (PHQ)-2 and/or the Generalized Anxiety Disorder (GAD)-2 as a part of routine antenatal care. Women who show symptoms perinatal depression or anxiety will be asked to complete the Edinburgh Postnatal Depression Scale (EPDS) and/or the Self-Reporting Questionnaire (SRQ)-20 with a trained psycho-social counselor to confirm symptoms (Appendix 2). Women who screen positively on either the PHQ-2/GAD-2, the EPDS (≥ 10), or SRQ-20 (≥ 8) will be invited to participate. Women screening positive for depression who choose not to participate will be referred to a mental health provider for care.

Study Visits (n=2 for participants in all arms)

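### Depression-screen entry is stated under three conflicting rules, and the 6-month SRQ-20 case outcome uses >8 where the protocol's cut-point is 8 or more

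*Combined protocol and SAP*

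**What the plan says.** **Entry.** Three rules stand in the current text.

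- *Rule 1.* The inclusion list in F4 reads "Screened positive for depression with a score ≥ 8 on the SRQ-20" and names no other instrument.
- *Rule 2.* The F4 narrative directly above that list accepts an EPDS score of at least 10 "and/or ≥ 8 on the SRQ-20 will be considered to be depressed and will be invited to participate". J.1.a (Human Subjects Involvement and Characteristics) is similar, without thresholds: participants are women who "screen positive for mental health disorders during pregnancy on the EPDS or SRQ-20 questionnaires".
- *Rule 3.* F8 (Screening and Enrollment) says "Women who screen positively on either the PHQ-2/GAD-2, the EPDS (≥ 10) or SRQ-20 (≥ 8) will be invited to participate". J.1.b repeats this: "Women who screen positively on either the PHQ-2/GAD-2, the EPDS (≥ 10), or SRQ-20 (≥ 8) will be invited to participate". J.2.a (Recruitment and Informed Consent) lists the same instruments and thresholds, and states that consenting women positive on any of them are enrolled.

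On procedure, F8 says that women with symptoms on the PHQ-2/GAD-2 "will be asked to complete the Edinburgh Postnatal Depression Scale (EPDS) and/or the Self-Reporting Questionnaire (SRQ)-20", as a step to confirm those symptoms.

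**Outcome.** F9.b defines the 6-month SRQ-20 outcome as the proportion scoring >8. In the same section, remission within the composite requires a fall of at least 50% from baseline and a score <8. The Baseline Visit text in F8 and J.1.b gives the cut-point for probable common mental disorder as 8 or above.

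**Who is analysed.** F4 records that "we have recruited a total of 12 women from our original 3 clinics". All 92 women count towards feasibility and acceptability, but "only the new 80 women will contribute to between-arm comparisons due to the differences in sites".

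**The concern.** The entry rules admit different women, and no passage says which one governs. F9.a makes the number enrolled, its comparison with the planned number and the reasons for non-enrolment part of the primary feasibility outcome. The same screened woman can count as an enrolment under one section and as ineligible under another. F9.a sets no pass/fail enrolment threshold, so no go/no-go decision turns on this. What suffers is the meaning of the feasibility figures for planning the later trial.

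Rules 2 and 3 also reach the secondary outcomes. They let a woman enter with SRQ-20 below 8. She is then a non-case, and inside the <8 limit for remission, before any treatment.

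The >8 definition is a separate defect and would remain if entry were settled. It classes women at the protocol's own cut-point as non-cases at 6 months.

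**Working it through.** No sample size, power or error rate in the plan depends on this point, so there is no stated figure to reproduce. The only count involved does add up: 12 + 2 × 40 = 92.

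**Step 1: entry rules over all screen results** (thresholds from F4 and F8: EPDS ≥10, SRQ-20 ≥8)

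| PHQ-2/GAD-2 | EPDS ≥10 | SRQ-20 ≥8 | Rule 1 | Rule 2 | Rule 3 |
|---|---|---|---|---|---|
| + | + | + | in | in | in |
| + | – | + | in | in | in |
| + | + | – | out | in | in |
| + | – | – | out | out | in |
| – | + | + | in | in | in |
| – | – | + | in | in | in |
| – | + | – | out | in | in |
| – | – | – | out | out | out |

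Over all 8 rows the rules admit 4, 6 and 7. F8 sends women with PHQ-2/GAD-2 symptoms on to the EPDS and/or SRQ-20, so the first 4 rows matter most. There the rules admit 2, 3 and 4.

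Two examples:
- EPDS 10 and SRQ-20 7: ineligible under Rule 1, eligible under Rules 2 and 3.
- Positive PHQ-2/GAD-2, EPDS 9 and SRQ-20 7: eligible under Rule 3 only.

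The documents do not give the share of women in each row, so these counts show where the rules part, not how many women are affected.

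**Step 2: which instruments are completed before entry.** F8 has the EPDS and/or the SRQ-20 at confirmation. The research-assistant paragraph of the Budget Justification describes screening with both. The SRQ-20 is collected at the baseline visit, but the protocol text does not say that every woman must have it scored before enrolment.

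**Step 3: the 6-month outcome**

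| SRQ-20 at 6 months | Entry threshold ≥8 | Case as written, >8 | Remission limit <8 |
|---|---|---|---|
| 7 | no | no | met |
| 8 | yes | no | not met |
| 9 | yes | yes | not met |

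Over scores 0 to 20, 8 is the only value that is neither a case nor inside the remission limit. With ≥8 no such value remains.

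Size, with 40 women assessed per arm:
- Shift in an arm's proportion per woman scoring 8: 1/40 = 2.5 percentage points.
- Shift in the between-arm difference: 2.5 × (number at 8 in one arm − number at 8 in the other). Equal numbers give 0. As an illustration, 3 against 1 gives 2.5 × 2 = 5.0 points.

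**Step 4: low baseline scores.** Improvement is (baseline − 6-month score)/baseline. It is undefined at a baseline of 0, which only Rules 2 and 3 permit.

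**The case against.** **Invitation is not enrolment.** The F4 narrative, F8 and J.1.b say who is invited, and only F4 has a list headed as inclusion criteria. A broad invitation narrowed by a formal criterion would be ordinary, and J.2.a starts consent only after eligibility is determined. This fails because J.2.a goes on to say that consenting women positive on any of the listed measures are enrolled. The F4 narrative also describes the women to be included, not only those to be approached.

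**One visit.** J.1.b treats screening, enrolment and baseline as a single visit, at which both EPDS and SRQ-20 are collected. The data collection instrument in Appendix 2 may settle the order, and it was not available here. The Budget Justification is not a procedure. This weakens Step 2 but does not touch the conflict between the rules.

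**Little divergence, no bias.** Three research assistants screen across all five clinics, so sites may in practice follow one rule. Individual randomisation at the two new sites means a loose entry rule does not bias the between-arm comparison. Both points stand. The feasibility counts would still need that rule to be stated.

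**The >8 is a slip of little consequence.** F10 also plans generalized linear models for SRQ-20 scores, which the cut-point does not affect if scores are analysed as a scale. The composite already uses <8. Case and remission are not complements in any event: a fall from 10 to 7 is a 30% improvement, so that woman is neither a case nor remitted under >8 or ≥8. The 2.5 points assumes complete follow-up; with 28 of 40 assessed (an assumption), one woman is 1/28 = 3.6 points, and unequal denominators break the simple net rule. All of this limits the impact. None of it makes >8 agree with a cut-point of 8 or above.

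**Conclusion.** Both inconsistencies hold and should be fixed. Neither threatens the validity of the randomised comparison.

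On entry, the number of women affected cannot be estimated from the documents. The consequence is for interpreting the primary feasibility counts, and it extends to the 12 women already recruited because they count towards feasibility.

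On the outcome, the definition is wrong as written. If it is coded literally, a woman who enters at 8 and does not change is reported as a non-case. The error is 2.5 points per such woman in a fully followed arm of 40, and zero in the difference when the arms have equal numbers at 8. It concerns a secondary outcome that F11 says will be read cautiously.

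**What to change.** 1. Reconcile the entry passages into one rule of the investigators' choosing. State it identically in F4 (narrative and list), F8, J.1.a, J.1.b and J.2.a, and say which instruments every woman completes before enrolment.
2. State which rule was applied to the 12 women already recruited.
3. In F9.b, change the SRQ-20 case definition from >8 to ≥8.
4. If the chosen rule admits women with SRQ-20 below 8, report their number in each arm and state how a baseline of 0 is handled in the composite. Keep all 80 individually randomised women in the between-arm comparisons.

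The cost is protocol wording, any ethics review the amendment needs, and at most one extra count per arm. No woman leaves any analysis. If the investigators choose a rule narrower than the one now in use, recruitment could slow; that trade-off is theirs. The outcome correction changes one symbol.
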